## 10 SAFETY & REPORTING

It is important to assess safety over the course of this study. This section describes in detail how safety is assessed, reporting of Adverse Events, Serious Adverse Events, and Unanticipated Problems. This section is a reference for internal use.

### 10.1 SAFETY PARAMETERS

**STIMULATION SIDE EFFECTS.** A stimulation adverse effects questionnaire used in previous studies will be administered at the end of each stimulation. This questionnaire will be used as a safety measure and to collect data on participant experience. The adverse effects questionnaire asks participants to respond on a 4-point Likert scale on the severity of symptoms experienced during the stimulation session (1 = absent, 2 = mild, 3 = moderate, 4 = severe). The side effects listed are headache, neck pain, scalp pain, tingling, itching, ringing/buzzing noise, burning sensation, local redness, sleepiness, trouble concentrating, improved mood, worsening of mood, dizziness, flickering lights, and

other (specify). Participants are also asked to rate on a 5-point Likert scale how related they believe the side effects to be to stimulation (1 = no relation, 2 = remote, 3 = possible, 4 = probable, 5 = definite).

## 10.2 METHODS AND TIMING FOR ASSESSING, RECORDING, AND ANALYZING SAFETY PARAMETERS

### 10.2.1 ADVERSE EVENTS

All AEs, including local and systemic reactions not meeting the criteria for “serious adverse events”, will be captured on the appropriate CRF. In addition, the AE Report Form will be completed by the researcher (Appendix B). The AE Report Form includes the following:

- What is known about the stimulation
- What is known about previous reported side effects
- If the AE occurred in temporal relation to the stimulation
- Whether or not the AE improves or disappears when stimulation is stopped
- Whether the AE is worsening of baseline symptoms
- Whether the AE is related to concurrent medical condition or medication use

Once complete, this form will be given to the PI, who will review, comment, and sign this form. Completed forms will be placed in the participant’s folder.

In addition, the researcher will document any AE occurrence on the AE log (*Appendix D*), which includes information such as the date of the AE, severity, relationship to the treatment (assessed by the PI\*), actions taken, and outcome(s). The log will be reviewed and initialed by the PI within 10 work days after being completed. All AEs will be followed to adequate resolution and will be graded for severity and relationship to study. Any medical condition noted at the stimulation session will be considered at baseline and not reported as an AE.

**\*Relationship to Study Products:** The PI will determine whether an AE is associated with the study treatment. The event will be labeled associated if the event is temporally related to the administration of a therapy and no other factors can explain the event. The event will be labeled as not associated if the event is temporally independent of the study treatment and can be explained by external factors, such as major life events.

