### Session 4 and 5: Stimulation 1 and 2 (3 hours)

- Motor thresholding using single pulse TMS for use in future sessions will be performed once for each participant on the first day of stimulation, and held constant for the following stimulation session.
- Before practice and performance of the cognitive control task, the TMS coils will be positioned over the targeted region.
- During performance of the task, stimulation will be delivered on every trial.

CONFIDENTIAL

- During stimulation, white noise will be played for the participants to reduce neural effects of auditory entrainment of rhythmic TMS.
- At the end of the session, participants will receive \$40, and \$60 in compensation for sessions 4, and 5, respectively.

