## 6 STUDY PROCEDURES/EVALUATIONS

### 6.1 SELF-REPORT MEASURES

Researcher will use a standard questionnaire to screen TMS & MRI candidates. The following questions include the standard contraindications for TMS & MRI research. The TMS contraindications assessment will be administered during the verbal phone screening and for every session prior to stimulation (sessions 4 and 5).

1. Do you have epilepsy or have you ever had a convulsion or a seizure?
2. Have you ever had a fainting spell or syncope? If yes, please describe in which occasion(s)
3. Have you ever had severe (i.e., followed by loss of consciousness) head trauma?
4. Do you have any hearing problems or ringing in your ears?
5. Are you pregnant or is there any chance that you might be?
6. Do you have metal in the brain/skull (except titanium)? (e.g. splint, fragments, clips, etc.)
7. Do you have cochlear implants?
8. Do you have an implanted neurostimulator? (e.g., DBS, epidural/subdural, VNS)
9. Do you have a cardiac pacemaker or intracardiac lines or metal in your body?
10. Do you have a medication infusion device?
11. Are you taking any medications? (Please list)
12. Did you ever have a surgical procedure to your spinal cord?
13. Do you have spinal or ventricular derivations?
14. Did you ever undergo TMS or MRI in the past?

Affirmative answers to one or more of questions 1–13 do not represent absolute contraindications to TMS and fMRI, but the risk/benefit ratio should be carefully balanced by researcher.

In addition to our screening form, we will administer the MRI screening form provided by the Biomedical Research Imaging Center (BRIC) at the University of North Carolina at Chapel Hill. After completion of this form, it is sent to lab technicians at the BRIC who provide additional screening of participants (this form is included in the Appendix). The MRI safety form is completed verbally during phone screening and in person during session 3 (MRI).

In addition, several self-report measures will be collected throughout this study. These measures are listed below and can be found in the attached documents.

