## 6.2 SPECIAL ASSAYS OR PROCEDURES

Each participant will receive stimulation in the fourth and fifth sessions, separated by about one week. Motor thresholding will take place in the first stimulation session. For stimulation day, the rhythmic TMS trains are delivered on every trial of the task (there are 600 trials per session). Each train of TMS consists of 5 pulses. There will be a total of 3000 pulses delivered per session in phase one, and with two coils there will be total of 6000 pulses per session in phase two. Each TMS train will be separated by a minimum of 5 seconds. There are three possible trains: individual alpha frequency with an approximate 100 milliseconds inter-pulse interval, individual theta frequency with a 200 milliseconds inter-pulse interval, and arrhythmic with a variable inter-pulse interval (with a minimum of 20 milliseconds inter-pulse interval). The inter-pulse interval, inter-train interval, number of trains, and TMS intensity are all under the safety guidelines set forth by Rossi et al. 2009 and is typical for experiments that deliver online TMS (Hanslmayr et al. 2014; Albouy et al. 2017).

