## APPENDIX B: AE REPORT FORM

### Adverse Effects Report:

*Reasons for Report (adverse event, time, date and place of occurrence if available):*

1. What do we already know about the stimulation?
  - a.
2. What is the temporal relationship of the AE to the stimulation?
  - a.
3. Does the AE improve or disappear when the stimulation is stopped?
  - a.
4. Is the AE a worsening of baseline symptom(s)?
  - a.
5. Is the AE a result of an underlying concurrent medical condition(s) or concurrent medication(s)?
  - a.
6. Additional Information provided by research team
  - a.

Research team member signature \_\_\_\_\_ Date \_\_\_\_\_

Co-Investigator:

---

---

---

---

---

Steps to be taken (if applicable)

---

---

---

---

Co-I signature \_\_\_\_\_ Date \_\_\_\_\_

PI Comments:

---

---

---

---

Steps to be taken (if applicable)

---

---

---

---

PI signature \_\_\_\_\_ Date \_\_\_\_\_

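### Section 10.2.1 fixes the AE baseline at a stimulation visit with no pre-TMS cut-off and no session number, so its literal wording drops some non-serious AEs

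*Combined protocol and SAP*

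**What the plan says.** The rule is one sentence in section 10.2.1 (Adverse Events): "Any medical condition noted at the stimulation session will be considered at baseline and not reported as an AE". It refers to a single stimulation session without a number, and it carries no wording about before or after TMS.

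The same section says that every AE, including those that are not serious, is captured. AE status brings four things: the AE report form, the PI's judgement on relationship to treatment, an entry in the AE log, and follow-up until the event is resolved. The form records "If the AE occurred in temporal relation to the stimulation", "Whether or not the AE improves or disappears when stimulation is stopped" and "Whether the AE is related to concurrent medical condition or medication use", and also whether a baseline symptom has worsened. Appendix B repeats these items, for example "What is the temporal relationship of the AE to the stimulation".

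On timing, section 6.2 says: "Each participant will receive stimulation in the fourth and fifth sessions, separated by about one week". Section 5.2 adds that motor thresholding "will be performed once for each participant on the first day of stimulation", so the first TMS pulse a participant receives is in session 4. Section 6.1 has the contraindication check done by phone and "for every session prior to stimulation (sessions 4 and 5").

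Section 9.1 says AEs are defined in the document. I found a definition of an SAE in the text, but no definition of an AE or AE onset window that would narrow the sentence. Section 5.2 uses the name Baseline for session 2, which precedes all TMS.

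**The concern.** A baseline for treatment-emergent events should close when exposure begins. Here it is tied to a visit at which exposure takes place, and one of the two visits that fit the description comes after an earlier exposure. Two kinds of non-serious event are at risk: those that begin while TMS is being given, and those that begin in the week after session 4 and come to light at session 5.

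The second kind matters because Appendix A lists no visit after session 5. Session 5 is therefore the only scheduled visit at which a delayed effect of session 4 could be noticed. Hearing is a concrete example. The contraindication check asks about hearing problems and ringing in the ears, and section 8.2.1 (Physical) discusses hearing loss as a risk of TMS, although it calls that risk theoretical, links it to prolonged exposure and provides ear protection.

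At stake is the completeness of the non-serious AE record. Section 9.4 also lists severe AEs and a rising frequency of events among the possible triggers for a safety review, and such a review relies on that record. No efficacy analysis in section 11 uses AE data.

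**Working it through.** No alpha, power or event count enters, and the plan states no figure to reproduce. The check is to apply the sentence to each possible onset under three readings.

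- Reading A (probable intent): illness present before any study TMS.
- Reading B (literal, session 4 only).
- Reading C (literal, sessions 4 and 5).

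| Non-serious condition | A | B | C |
|---|---|---|---|
| Present before session 4 TMS, noted at session 4 | Baseline | Baseline | Baseline |
| Begins during session 4 after TMS has started, noted there | AE | Not an AE | Not an AE |
| Begins after session 4, first noted at session 5 | AE | AE | Not an AE |
| Begins during session 5 after TMS has started, noted there | AE | AE | Not an AE |
| Begins after session 4, reported by phone or email before session 5 | AE | AE | AE |

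**Step 1: the literal readings conflict with the rest of the section.** Row 2 fails under both B and C. Section 10.2.1 says all AEs are captured, and its form asks about timing relative to stimulation and about improvement once stimulation stops. Those items have a purpose only if conditions that start during stimulation can be AEs.

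**Step 2: the session 5 consequence is conditional.** Rows 3 and 4 fail only under C. The text does not choose between B and C.

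**Step 3: do other routes restore the four AE steps?**

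- *Serious events* (section 10.2.1, Serious Adverse Events): captured on their own form and log throughout participation. Non-serious events are not covered.
- *Severe questionnaire ratings* (sections 8.3 and 9.2): go to an adverse events form and the log. This covers questionnaire answers only.
- *Unexpected events* (section 10.2.2): logged and sent to the IRB. An effect that the protocol already describes may not count as unexpected.
- *Reporting to the PI* (section 9.1): the PI hears of the event, but section 10.2.1 still classes it as not an AE.
- *Side-effect questionnaire* (sections 6.3 and 10.1): given at the end of sessions 4 and 5, with severity and perceived relatedness. It asks about symptoms during the session. Ringing that persists into session 5 could be rated there, but its onset after session 4 would not be recorded.

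None of these gives a non-serious, non-Severe, not unexpected condition the form, causality assessment, log entry and follow-up that AE status brings.

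**The case against.** The strongest reply is that the sentence is loosely worded and nobody would apply it literally. It speaks of medical conditions, and the form list uses a similar phrase for a background cause of an AE, which points to pre-existing illness. The form item on worsening of baseline symptoms shows that the section already separates baseline from later change and treats worsening as a possible AE. On that intent, a condition that starts after session 4 TMS is plainly not baseline. Participants can also contact staff between visits (section 3.3.2) and receive a reminder at least 24 hours before each session (section 5.1). Anything raised then has not been noted at a stimulation session.

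The argument about intent is sound as far as it goes, and it limits the point. It does not remove it: nothing in the documents states that limit, and staff who follow the words would reach the wrong classification.

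A reader might go further and infer that a condition first noted at session 5 is definitely not an AE under this plan. The documents do not support that. The session is given in the singular without a number; if session 4 alone is meant, that example falls away and only the in-session conflict at session 4 remains.

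A reader might also infer that sections 8.3 and 9.2 confine the AE form to Severe ratings and so contradict section 10.2.1. They do not. They state a step for Severe ratings without taking milder AEs off the form that section 10.2.1 requires for all AEs.

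**Conclusion.** The point holds in a limited form. As written, the sentence takes AE status from non-serious conditions that begin during a stimulation session, against the same section's coverage of all AEs. If it extends to session 5, it also takes AE status from conditions that arise after session 4 TMS and are first noted at session 5. The first consequence rests on reading the words literally; the second rests in addition on the unnumbered session including session 5.

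The effect is on the completeness of non-serious AE records. Serious events, Severe ratings and unexpected events remain captured. The size is unknown because the documents give no event rate.

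A reader might be tempted to size it from planned exposure: 48 completers per phase x 2 phases = 96 intervals of about one week, or about 96 participant-weeks. That is follow-up time, not a count of lost events. It applies only if session 5 is included, and it contains conditions that would be reported before session 5 and so recorded as AEs. It should not be quoted as the size of the problem.

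This is a correction worth making for the safety record. It does not bear on the primary or secondary analyses.

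**What to change.** Replace the sentence in section 10.2.1 with a cut-off tied to first exposure, for example: *Baseline conditions are those recorded before the first TMS pulse of session 4, that is, before motor thresholding. A condition that begins or worsens after that pulse, including between sessions 4 and 5, is recorded as an AE.*

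To apply it, compare each participant's pre-stimulation answers at session 5 with those given at session 4, and ask when any new or worse condition began. A line on the session 5 checklist is enough. The contraindication check is already done before stimulation at both sessions, so no new assessment is needed. The comparison reaches only what that check asks or the participant volunteers.

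The cost is one sentence, one checklist line, and slightly more AE paperwork and PI sign-off.

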### 10.2.1 SERIOUS ADVERSE EVENTS

**Serious Adverse Event (SAE):** An SAE, as defined by the NIH, consists of adverse events that result in death, require either inpatient hospitalization or the prolongation of hospitalization, are life-threatening, result in a persistent or significant disability/incapacity or result in congenital anomaly/birth defect. Other important medical events, based upon appropriate medical judgment, may also be considered Serious Adverse Events if a trial participant’s health is at risk and intervention is required to prevent an outcome mentioned. Importantly, an SAE is any event of this kind that occurs within the time frame of study participation without any direct relationship to the study intervention itself.

All SAEs will be recorded on the Serious Adverse Events Form (*Appendix B*), documented in the UE/SAE log and reported to the IRB. The SAE Form will be completed by the researcher, and includes information relating to the onset and nature of the SAE, relationship to the study treatment, seriousness of the SAE, treatment required as a response to the SAE, and outcome. This form will be filed in the participant’s folder at the resolution of the event. The researcher will complete the UE/SAE log (*Appendix D*) which includes information such as the date of the event, time at which the study team was informed of the event, details, when the IRB was notified, and the date that the SAE form was completed.

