## 9.2 SAFETY OVERSIGHT

Safety oversight will be under the direction of the PI, who will review AEs in real time and make decisions regarding a participant's continuation of the clinical trial.

There is a theoretical likelihood that stimulation of neuronal circuits can lead to epileptic discharge. To minimize this occurrence, we screen and exclude participants with personal and family history of neurological conditions from the study. Nonetheless, there is an extremely rate, but non-zero, chance that a seizure may occur.

1. Move the participant into a supine position if possible (the TMS chair can recline to achieve this position). Move everything away from the participant, so the participant cannot accidentally injure himself/herself while seizing. Do NOT try to restrain the participant or put things in the participant's mouth. Call 911 as soon as possible.
2. When the participant stops seizing, lay them on their right side with their head resting on their right arm.
3. When the participant is aware, explain that they had a seizure, which is a possible side effect of the study, but that having a seizure does not mean that they have epilepsy or will have long term changes in health/brain damage.
4. Wait for the EMTs to arrive. Call the medical monitor, [name], and follow any instructions. Call the PI and inform them of the event.

If abnormalities or a seizure is witnessed during the course of the study, [name] MD from the Department of Neurology will assist the participant in scheduling a follow-up appointment if she determines it to be necessary. In the theoretical event that a seizure is witnessed that involves the loss of consciousness, the participants will be told not to operate a motor vehicle until cleared by the DMV. All researchers are trained in First Aid which includes response to seizure. In addition, our TMS training module includes seizure response (see steps above). In the event of a seizure, a serious adverse event will be reported.

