### 10.3 REPORTING PROCEDURES

We will be adopting the following table for reporting procedures:

What Event is Reported	When is Event Reported	By Whom the Event is Reported	To Whom the Event is Reported
Fatal or life-threatening unexpected, suspected serious adverse reactions	Within 24 hours of initial receipt of information	Investigator	Local/internal IRBs
Non-fatal, non-life threatening unexpected, suspected serious adverse reactions	Within 10 working days of initial receipt of information	Researcher	Local/internal IRBs/Institutional Officials, DSMB
Unanticipated adverse device effects	Within 10 working days of investigator first learning of effect	Investigator	Local/internal IRBs
Unanticipated problem that is not an SAE	Within 10 working days of the investigator becoming aware of the problem	Investigator	Local/internal IRBs/Institutional officials
All Unanticipated Problems	Within 30 working days of the IRB's receipt of the report of the UP from the investigator	IRB	OHRP
		Investigator	External IRBs

CONFIDENTIAL

---

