### 10.4 TYPES AND DURATION OF FOLLOW-UP OF PARTICIPANTS AFTER ADVERSE EVENTS

Medical monitors and PI will follow up with participants within ten working days of an SAE that is related to stimulation.

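### Read literally, the SAE definition in section 10.2.1 leaves out serious events caused directly by stimulation, contradicting sections 9.2, 10.3 and 10.4, Appendix D and its own SAE form

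*Combined protocol and SAP*

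**What the plan says.** Two sections of the combined protocol and SAP carry the number 10.2.1. Unless stated otherwise, 10.2.1 here means the one headed Serious Adverse Events.

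- **10.2.1, opening sentence.** "An SAE, as defined by the NIH, consists of adverse events that result in death", followed by the other usual outcomes. No causality condition is attached.
- **10.2.1, closing sentence of the definition.** Flagged as important, it describes an SAE as one of these events that "occurs within the time frame of study participation without any direct relationship to the study intervention itself".
- **10.2.1, next paragraph.** All SAEs go on the SAE form and the UE/SAE log and are reported to the IRB. The form holds "information relating to the onset and nature of the SAE, relationship to the study treatment, seriousness of the SAE", among other items.
- **9.2 Safety Oversight.** After a seizure, staff are to "explain that they had a seizure, which is a possible side effect of the study". The section also states: "In the event of a seizure, a serious adverse event will be reported".
- **10.3 Reporting Procedures.** The first row of the table covers "Fatal or life-threatening unexpected, suspected serious adverse reactions".
- **10.4.** The medical monitors and PI will "follow up with participants within ten working days of an SAE that is related to stimulation".
- **Appendix D.** The log has a tick box for seriousness beside a four-level relationship scale whose first level is related.
- **9.4 Termination of Study.** The total number of SAEs, and the number of a given type, are among the examples of findings that might prompt a safety review.

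**The concern.** A definition of seriousness should turn on outcome, with causality recorded separately. Here the closing sentence puts a causality condition inside the definition, and it points the wrong way: an unrelated hospital admission qualifies, while one caused directly by stimulation does not.

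The SAE label decides whether an event goes on the SAE form and the UE/SAE log, is reported to the IRB as an SAE, receives the 10.4 follow-up, and enters the counts mentioned in 9.4. Section 9.1 says that AEs and SAEs are clearly defined in the protocol, and section 10 describes itself as a reference for internal use. Staff are therefore expected to classify events from this text as it stands.

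**Working it through.** No arithmetic applies and the plan gives no figure to reproduce. The check compares the definition with every place that relies on the SAE class.

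**Step 1. Does the rest of the plan assume that a directly related event can be an SAE?**

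- *Opening sentence of 10.2.1:* yes. It lists outcomes only.
- *SAE form in 10.2.1:* yes. A relationship field has little use if directly related events are excluded beforehand.
- *9.2:* yes. It calls seizure a possible side effect of the study and has it reported as an SAE.
- *10.3:* yes. A suspected serious adverse reaction is a serious event thought to be caused by the intervention.
- *10.4:* yes. It selects the SAEs that are related to stimulation.
- *Appendix D:* yes. The same row can be marked both serious and related.

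All six conflict with the literal closing sentence. No other text in the document corrects it.

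**Step 2. Which events would be lost if the sentence were applied literally?**

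| Serious event | SAE on the literal reading? | Routes that remain |
|---|---|---|
| Unrelated to TMS | Yes | All SAE routes |
| Indirectly related to TMS | Yes, because only a direct relationship is excluded | All SAE routes, including 10.4 |
| Seizure | Named as an SAE by 9.2 | 9.2 reporting; hold and stop rules in 9.4 |
| Directly caused, unexpected | No | IRB through 10.2.2 and 10.3; UE/SAE log through 10.2.2; AE recording |
| Directly caused, anticipated, not seizure | No | AE recording only |

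AE recording is set by the other section 10.2.1 (Adverse Events): CRF, AE report form, AE log, PI review, a relationship grade, and follow-up until the event resolves.

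**Step 3. Can the last row occur?** The 10.3 rows for reports by the study team are confined to unexpected reactions, unanticipated device effects and unanticipated problems. Section 10.2.2 is likewise confined to the unexpected. Section 8.2.1 (Physical) names hearing damage from TMS as a theoretical risk. If that led to lasting disability, it would meet the outcome criteria of 10.2.1, yet it is a described risk and might not count as unexpected. Section 10.2.2 allows an event to be unexpected in severity or frequency as well as in nature, so some such events would still be caught. The row is small, but the protocol's own risk list shows that it can be filled.

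**The case against.** The strongest reply is that the sentence can be read the other way. It speaks of any event of the listed kind, which widens the scope, and its last phrase can be taken to mean that no direct relationship is *required*. On that reading the relationship field, 9.2, 10.4 and Appendix D show how the sentence should be understood, and a trained researcher would not leave out an admission caused by stimulation.

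This stands as an account of intent. It does not rescue the wording, which states absence of a relationship rather than indifference to it. A safety definition should not depend on four other places to reverse its plain sense.

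The second reply, that other routes exist, also largely stands. A reader might infer from the sentence that every stimulation-caused event except seizure escapes IRB reporting. The documents do not support that: unexpected events reach the IRB through 10.2.2 and 10.3, and 9.1 has all AEs and SAEs discussed with the PI.

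A reader might also infer that the class followed up under 10.4 is empty. That goes too far, because 10.2.1 excludes only a *direct* relationship while 10.4 says only that the SAE is related.

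Third, section 11 contains no analysis of SAE counts, and 9.4 offers those counts only as examples, alongside severe AEs and rising frequency. Its explicit hold and stop rules rest on seizures. This stands too: no efficacy or planned safety analysis is affected.

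**Conclusion.** The definition is wrong as written and contradicts the provisions around it. The contradiction is certain from the text; the practical exposure is narrow. It covers anticipated serious events, other than seizure, that stimulation causes directly. Applied literally, 10.2.1 would keep these off the SAE form and the UE/SAE log, out of SAE reporting to the IRB, out of the 10.4 follow-up, and out of the SAE counts cited in 9.4. They would still be recorded and followed as AEs.

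The conclusion assumes that staff could apply the sentence literally; the documents do not show that anyone has. They give no expected SAE rate. I assume that few such events will occur in healthy adults, and I put no number on them.

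A reader might see in the wording a plan to leave out device-related harm. The outcome-based opening, the relationship field and the seizure rule all point the other way. This is a drafting defect. It merits correction in the next amendment because it sits in an operative safety rule.

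**What to change.** In section 10.2.1 (Serious Adverse Events), replace the end of the quoted sentence, from the word 'without' onward, with *whether or not it is related to the study intervention*. Keep relationship to treatment as a separate item on the SAE form, where it already is. The definition then agrees with 9.2, 9.4, 10.3, 10.4 and Appendix D.

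Section 10.4 needs no rewording for this purpose and should stay as the sponsor wrote it. This point takes no view on its interval or on who should be followed.

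The cost is one phrase in the next amendment and a note to the staff who classify events. Visits, stimulation, data collection and analysis do not change.
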